9.1. Definition

Adverse Event (AE)

An adverse event (AE) is defined as any unfavorable and unintended sign, symptom or disease, regardless of whether it is considered related to the medical device or procedure that occurs during the course of the study.

In all cases, etiology will have to be researched and identified as soon as possible.

Serious Adverse Event (SAE)

A serious adverse event (SAE) is defined as any untoward medical occurrence that results in death, is life threatening, requires inpatient hospitalization or prolongation of existing hospitalization, results in persistent or significant disability/incapacity, or is a congenital anomaly/birth defect.

The investigator is responsible of transmission of SAE to the promoter and the promoter is responsible of transmission of the SAE declaration to the authorities.

9.2. Gradation

Adverse events should be categorized by the investigator according to severity:

- **Mild:** perception of sign or symptom, but **easily tolerated**.
- **Moderate:** **cumbersome** enough to impact subject activities.
- **Severe:** modifying **considerably** patient activities, or **impairing**, or constituting a **threat for the life** of the patient.

9.3. Causality

Main factors to take into account to determine the causality are:

- Events chronology,
- AE evolution when the product is not used anymore or used again,
- Existence of another etiology that could explain the AE,
- Existence of similar published or known AE.

9.4. Expected AE

The expected AEs of the Cefaly® are:

- Reversible skin irritation at the place of electrode
- Allergic reaction to the gel of the electrode (1 out of 1000)
- Headache after the session (0.52%)
- Feeling of fatigue

9.5. AE collection

The patients are instructed to report all AEs to the investigator during the 2 hours of the protocol. AEs will be analyzed by the investigator who will document it in the CRF.

All AEs will be collected in the CRF, specifying:

- Their nature
- Start date and duration
- Causality (according to investigator's opinion)
- Countermeasures and results

If the AE is a SAE, the promoter should be notified as soon as possible.

9.6. Investigator's responsibility with respect to a SAE.

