4.2. Experimental protocol

Patients having a stabilized migraine attack will be recruited during a standard care visit or at an on-demand appointment. They will report their pain score before the treatment (recruitment phase), after 1 hour of treatment (acute treatment phase) and finally 2 hours after the beginning of the treatment (post-treatment phase). At that moment (2 hours after the beginning of the treatment), patients will receive rescue medication if necessary. Rescue medication intake will be reported during the 24 hours following the beginning of the treatment. Pain score at 24 hours after the treatment will be reported as well. The overall study flow is illustrated in Figure 1. During the different phases the investigator will monitor adverse events.

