4.2.3. Post-treatment phase

Two hours after the beginning of the treatment the patient will have to give a new estimate of the pain on the VAS, provided that the patient didn't take a rescue medication before.

After the 2 hours, if needed usual rescue treatment can be administrated to the patient. If so, this is recorded by the investigator.

Patients will also be instructed to record the pain level 24 hours after the beginning of the treatment. They will be contacted to report this pain level and whether or not rescue medication was taken within the 24 hours following the beginning of the treatment. In case of rescue medication intake within the 24 hours following the treatment the pain level at 24 hours will not be taken into account.

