7.1. Measures

Pain score. In order to evaluate the modification of pain score from baseline to 1-hour treatment and to 2-hour treatment, patients will be asked to give an indication on the pain level using a visual analogue scale (VAS) counting eleven levels (0 = no pain, 10 = maximum pain) at the recruitment phase (before applying the treatment), right after the treatment phase (1 hour), 2 hours after the beginning of the treatment and at 24 hours after the beginning of the treatment.

Rescue medication after the treatment. The investigator will also record whether the patient uses another acute medication right after the 2 hours. Patients will also be contacted 24 hours after the beginning of the treatment to report whether or not rescue medication was taken within the 24 hours following the beginning of the treatment.

The following table depicts when the different measures will be made:

	Baseline	1 hour	2 hours	24 hours
Pain score	●	●	●	●
Rescue medication intake			●	●

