9.6.3. Monitoring

The monitoring is ensured until total recovery, stabilization or death of the patient, on common decision of the monitor and the investigator. Related costs are covered by the promoter.

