9.6.4. Notification period

It is the investigator responsibility to notify the promoter about any SAE occurring:

- During the whole study period
- At any time, after the end of the study if the investigator thinks this could be related to the device under test during the study (if no other cause than the research could reasonably explain it).

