9.7. Notification by the promoter to the authorities

In case the promoter is notified of an unexpected AE, he will report it directly to the national competent authority (FDA) and to the relevant central Investigational Review Board (Columbia University IRB).

Similarly, if a new fact relevant to the study or to the device appears that could impact the safety of the subjects participating to the study, the promoter takes the appropriate emergency measures. The promoter also notifies both the FDA and the IRB of this new fact and of the taken measures.

The delay to inform the authorities will be 2 days in case of death or life threatening AE, and 15 days in case of other unexpected AE or new fact. An extra delay of 8 days is foreseen to provide a follow-up report.

If necessary, the investigator will ask the subjects participating to the study to confirm their consent based on the updated information.

10. List of Annexes

CRF

Informed consent

References

1. **BMC Neurol.** 2011 Oct 28;11:135. doi: 10.1186/1471-2377-11-135. Supraorbital transcutaneous neurostimulation has sedative effects in healthy subjects. Piquet M, Balestra C, Sava SL, Schoenen JE.
2. **Neurology.** 2013 Feb 19;80(8):697-704. doi: 10.1212/WNL.0b013e3182825055. Epub 2013 Feb 6. Migraine prevention with a supraorbital transcutaneous stimulator: a randomized controlled trial. Schoenen J, Vandersmissen B, Jeangette S, Herroelen L, Vandenheede M, Gérard P, Magis D.
3. **J Headache Pain.** 2013 Dec 1;14:95. doi: 10.1186/1129-2377-14-95. Safety and patients' satisfaction of transcutaneous supraorbital neurostimulation (tSNS) with the Cefaly® device in headache treatment: a survey of 2,313 headache sufferers in the general population. Magis D1, Sava S, d'Elia TS, Baschi R, Schoenen J.
4. **Cephalalgia.** 2009 Jan 29;29:1101-1172 doi: 10.1111/j.1468-2982.2008.01798_1.x Poster Abstracts. A pilot study on supra-orbital surface electrotherapy in migraine. Gérardy PY, Fabry D, Fumal A, Schoenen J.
5. **American Headache Society 56th Annual Scientific Meeting,** Los Angeles, CA. Poster presentation. Transcutaneous supraorbital nerve stimulation as a rescue therapy. Kozminski M.
6. Acute treatment of migraine attacks: efficacy and safety of a nonsteroidal anti-inflammatory drug, diclofenac-potassium, in comparison to oral sumatriptan and placebo. The Diclofenac-K/Sumatriptan Migraine Study Group. *Cephalalgia* 19, 232–40 (1999).

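### In the visible protocol text, section 9.5 asks patients for AEs only during the first 2 hours, so non-serious AEs between 2 and 24 hours are not solicited

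*Combined protocol and SAP*

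**What the plan says.** The visible instruction to patients on AE reporting is in section 9.5: "The patients are instructed to report all AEs to the investigator during the 2 hours of the protocol". The same section then says that all AEs go into the CRF, with nature, start date, duration, causality, countermeasures and results.

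Three other places bear on the time window:

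- Section 4.2: "During the different phases the investigator will monitor adverse events".
- Section 4.2.3, the post-treatment phase, includes a 24-hour pain record and a contact with the patient: "They will be contacted to report this pain level and whether or not rescue medication was taken within the 24 hours" after the start of treatment.
- Section 7.1 describes the same contact: "Patients will also be contacted 24 hours after the beginning of the treatment to report whether or not rescue medication was taken". Its schedule table has two rows, pain score and rescue medication.

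Section 3 lists pain change and rescue use at 24 hours among the secondary outcomes. For SAEs, section 9.6.4 sets a separate and wider window: "During the whole study period", and later if the investigator suspects the device. Section 8.2.2 promises a descriptive summary of safety data at each time point.

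**The concern.** The trial follows patients for 24 hours, but the instruction on AEs covers 2 hours, and the one later contact is not described as asking about them. Section 9.4 lists skin irritation, gel allergy, headache after the session and fatigue as expected, and nothing in the documents says that these begin within 2 hours. A returning headache would show in part through the 24-hour pain score and the rescue record. The other three would not.

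The later course of an event is also at stake. Section 9.5 wants duration and results for each AE, and section 9.3 counts how an event evolves once the device is off as evidence on causality. Stimulation lasts 1 hour, so a 2-hour window leaves 2 - 1 = 1 hour of observation off the device. If a non-serious AE is still present at 2 hours, no visible step finds out how it ended. Follow-up to resolution is promised in section 9.6.3 ("The monitoring is ensured until total recovery, stabilization or death of the patient"), but that text sits under the SAE heading.

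A reader of the final report could take the AE table as the 24-hour safety experience when solicitation had stopped at 2 hours.

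**Working it through.** The plan states no figure on this point, so the check is a comparison of passages.

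**1. Length of follow-up.** Sections 3, 4.2, 4.2.3 and 7.1 all carry pain and rescue data to 24 hours after the start of treatment.

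**2. Length of AE solicitation.** Section 9.5 gives 2 hours. The remainder is 24 - 2 = 22 hours, or 22/24 = 92% of follow-up, with no stated AE question. This is a share of time, not of events.

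**3. Content of the 24-hour contact.** Section 4.2.3 names pain level and rescue use. The text of 7.1 names rescue use at the contact, and its table adds the 24-hour pain score. Neither names AEs, and the table has no AE row.

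**4. Does another passage fill the gap?**

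| Section | What it covers | Fills 2 to 24 h for non-serious AEs? |
|---|---|---|
| 4.2 | AE monitoring in the different phases | Only if the post-treatment phase runs to 24 h; no method stated |
| 9.1 | Definition of an AE | No; it sets no collection schedule |
| 9.5, CRF sentence | All AEs recorded, no time limit | Only for events that are volunteered |
| 9.6.3, 9.6.4 | SAE follow-up and notification | No; SAEs only |

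**5. Effect on the AE rate.** Let f be the share of a reaction's events that start after 2 hours. Then

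solicited rate = (1 - f) × 24-hour rate.

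The documents give no onset times, so f may lie anywhere from 0 to 1 and the shortfall cannot be calculated.

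**6. The rates in 9.4 do not help.** Read as per-patient rates that hold for a 60-minute session (both are assumptions), they give 90 × 0.001 = 0.09 gel allergies in the whole trial. For post-session headache they give 45 × 0.0052 = 0.23 in the verum arm, or 90 × 0.0052 = 0.47 if sham has the same rate. These count events at any onset time. They show that few such events are expected, not how many would be late. No rate is given for skin irritation or fatigue.

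**The case against.** The best defence is that the protocol uses two hours as shorthand for the supervised part of the study. Section 6.6 describes the study as one hour of stimulation and one of observation, section 4.2.4 uses the same shorthand, and section 4.2 attaches the post-treatment label to the 2-hour score. On that usage, monitoring in the different phases matches 9.5 and there is no contradiction. This stands in part. A tension remains because 4.2.3 puts the 24-hour contact under the post-treatment heading. Even on the narrow reading, the 24-hour contact still omits AEs.

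A reader might infer a direct contradiction with section 9.1, which speaks of any event "regardless of whether it is considered related to the medical device or procedure that occurs during the course of the study". The documents do not support that: 9.1 defines what an AE is and does not say when patients are asked.

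Second, the CRF and the consent form are annexes that are not visible here. Either could contain a 24-hour AE question or a longer instruction to patients. This stands, and it limits the finding to the visible text.

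Third, a reader might infer that unexpected events would escape the regulatory route in 9.7, which is not confined to serious events and starts once the promoter is notified. That reaches little. The reactions in 9.4 are listed as expected, so the route would not ordinarily apply to them, and SAEs are covered by 9.6.4. Only late, non-serious, unexpected events remain, and the documents say nothing about how often they occur.

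Fourth, a reader might infer from 8.2.2 that patients outside its ITT definition are also dropped from the AE summary. The safety summary and the ITT sentence are separate bullets, so that reading is possible but not required. It is not part of this point.

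**Conclusion.** The point holds for the visible protocol text. Patients are asked for AEs during the first 2 hours, follow-up lasts 24, and the 24-hour contact as described leaves AEs out. Non-serious AEs starting between 2 and 24 hours, and the later course of those still present at 2 hours, therefore depend on the patient volunteering them. The summary under 8.2.2 would describe solicited events with onset within 2 hours.

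The size is modest and cannot be put as a number of events. Two stronger conclusions are tempting and unsupported. One is that late AEs go unrecorded altogether: 9.5 sends all AEs to the CRF without a time limit, and SAEs have their own rule. The other is that the gap biases the comparison between arms: nothing in the documents shows that late events would be missed more often in one arm. No efficacy result or sample size changes, and section 3 lists no safety outcome.

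The conclusion rests on two assumptions: that the unseen annexes contain no 24-hour AE question, and that 4.2.3 is right to treat the 24-hour contact as part of the post-treatment phase. If the first fails, only the wording of 9.5 and 7.1 needs to change. The second affects the tension with 4.2, not the omission at the contact.

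**What to change.** Align the window in 9.5 with 4.2 and 4.2.3. Add an AE question to the existing 24-hour contact, covering events that are new since 2 hours and the outcome of those ongoing at 2 hours. State it in 9.5, add an AE row to the table in 7.1, and check that the CRF has a matching line. In the report, give the AE collection window with the AE table.

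The cost is one question at a contact that already takes place, one table row and one CRF line. More events may be reported, and those that start after rescue medication will be harder to attribute to the device. Recording the time of onset next to the time of rescue would help with that.

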9.6.1. SAE Notification

Each SAE will be described on the specific form with as much detail as possible. The informations to be communicated to the promoter are:

- Patient identification
- AE severity
- Start and end date
- Detailed description
- AE evolution
- Current diseases and relevant medical history of the patient
- Patient received treatments
- Causality link with the device under test

The investigator should also join to the AE report, each time it is possible:

- A copy of the hospitalization report
- A copy of all complementary exam results performed, including relevant negative results and joining the laboratory reference values
- Or any other document that he/she found useful and relevant
- Possibly, a copy of the autopsy report

All documents will be made anonymous and will bear the identification number of the subject.

9.6.2. Modalities of notification to the promoter

All SAE, no matter its causality relationship with the device under test, should be declared by the investigator:

- To promoter (represented by the CEO)
- As fast as possible
- By e-mail: see the specific form in the CRF

9.6.3. Monitoring

The monitoring is ensured until total recovery, stabilization or death of the patient, on common decision of the monitor and the investigator. Related costs are covered by the promoter.

9.6.4. Notification period

It is the investigator responsibility to notify the promoter about any SAE occurring:

- During the whole study period
- At any time, after the end of the study if the investigator thinks this could be related to the device under test during the study (if no other cause than the research could reasonably explain it).

9.7. Notification by the promoter to the authorities

In case the promoter is notified of an unexpected AE, he will report it directly to the national competent authority (FDA) and to the relevant central Investigational Review Board (Columbia University IRB).

Similarly, if a new fact relevant to the study or to the device appears that could impact the safety of the subjects participating to the study, the promoter takes the appropriate emergency measures. The promoter also notifies both the FDA and the IRB of this new fact and of the taken measures.

The delay to inform the authorities will be 2 days in case of death or life threatening AE, and 15 days in case of other unexpected AE or new fact. An extra delay of 8 days is foreseen to provide a follow-up report.

If necessary, the investigator will ask the subjects participating to the study to confirm their consent based on the updated information.

10. List of Annexes

CRF

Informed consent

References

1. **BMC Neurol.** 2011 Oct 28;11:135. doi: 10.1186/1471-2377-11-135. Supraorbital transcutaneous neurostimulation has sedative effects in healthy subjects. Piquet M, Balestra C, Sava SL, Schoenen JE.
2. **Neurology.** 2013 Feb 19;80(8):697-704. doi: 10.1212/WNL.0b013e3182825055. Epub 2013 Feb 6. Migraine prevention with a supraorbital transcutaneous stimulator: a randomized controlled trial. Schoenen J, Vandersmissen B, Jeangette S, Herroelen L, Vandenheede M, Gérard P, Magis D.
3. **J Headache Pain.** 2013 Dec 1;14:95. doi: 10.1186/1129-2377-14-95. Safety and patients' satisfaction of transcutaneous supraorbital neurostimulation (tSNS) with the Cefaly® device in headache treatment: a survey of 2,313 headache sufferers in the general population. Magis D1, Sava S, d'Elia TS, Baschi R, Schoenen J.
4. **Cephalalgia.** 2009 Jan 29;29:1101-1172 doi: 10.1111/j.1468-2982.2008.01798_1.x Poster Abstracts. A pilot study on supra-orbital surface electrotherapy in migraine. Gérardy PY, Fabry D, Fumal A, Schoenen J.
5. **American Headache Society 56th Annual Scientific Meeting,** Los Angeles, CA. Poster presentation. Transcutaneous supraorbital nerve stimulation as a rescue therapy. Kozminski M.
6. Acute treatment of migraine attacks: efficacy and safety of a nonsteroidal anti-inflammatory drug, diclofenac-potassium, in comparison to oral sumatriptan and placebo. The Diclofenac-K/Sumatriptan Migraine Study Group. *Cephalalgia* 19, 232–40 (1999).
